9.7 DATA ANALYSIS

Descriptive analysis will be means, medians, quantiles, proportions (with their respective 95% confidence intervals and SE when relevant) and contingency tables according to the nature of the variables. As a dispersion measurement the standard deviation and the interquartile range will be calculated.

Statistical analysis will be performed using the SAS software.

The statistical analysis will be done on all evaluable patients i.e. patients who enter the study without inclusion-exclusion criteria violations and with at least one TSQM-9 domain score (effectiveness, convenience and global satisfaction) calculated. Enrolled patients not evaluable for analysis will be described in terms of frequency of violations and according main socio-demographic variables (such as age and gender), clinical (such as disease severity and number of exacerbations in the 12-month before enrollment) and treatment satisfaction scores (if available) at baseline.

Patients with missing values will not be excluded from the analysis, their data will not be replaced; frequency of missing data will be given for all analyzed variables. Lost to follow up patients will be analyzed until their last available visit.

Appropriate descriptive statistics for main socio-demographic (gender, age, race, education and employment status, smoking habits) and clinical variables (medical history for COPD and not, disease severity and awareness) at baseline visit will be presented to describe the study population at inclusion. Patients at inclusion in the study will be also described in terms of ongoing pharmacological and non pharmacological treatments for COPD.

Moreover, the study population will be described in terms of number of exacerbations occurred during study period and changes in COPD medication since baseline.

The study objectives will be evaluated as below described.

Primary objective

The patients' satisfaction for medical treatment will be assessed by the 9-item Treatment Satisfaction Questionnaire for Medication (TSQM-9) at each study visit (45, 46). TSQM-9 is a self-rated tool for evaluating patient satisfaction to medical therapy. It is composed by 3 domains covering efficacy, convenience and global treatment satisfaction. TSQM-9 scores will be calculated according to author's instructions and summarized at each time point on all evaluable patients. Patients lost to follow up will be considered until their last available visit.

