The patients switching treatment during observation period will not be excluded from analysis and will be evaluated at each visit as above described. Few patients are expected to stop treatment during study; if any, for primary objective evaluation they will be censored at the latest available visit. Comparisons of satisfaction between different treatment/devices are not matter of this study, throughout all analysis treatments will be lumped together.

Secondary objectives

#1 To describe patient disease perception (B-IPQ), adherence to COPD treatment (MMAS4), health status (CAT) and dyspnea (MMRC) during a 12-month observation period

A description of B-IPQ (consequences, timeline, personal control, treatment control, identity, concern, emotions and illness comprehensibility), MMAS-4, CAT and MMRC scores will be provided at baseline and at follow-up visits. Scale scores will be summarized at each time point. Patients lost to follow up will be considered until their last available visit. Missing items of questionnaires/scales will be replaced if applicable according to scoring algorithm [32-38].

#2 To analyse the relation between treatment satisfaction for medical treatment and demographic/clinical parameters and PROs during a 12-month observation period

Three regression models (one for each TSQM-9 domain score) will be estimated; the dependent variable will be domain score and the independent ones will be: age and gender (at enrollment), number of exacerbations, relevant spirometry parameters (such as FEV1, FVC, FEV1 % of the predicted, RV, TLC, DLCO), level of dyspnea (MMRC score), impact of COPD on a patient's life (CAT) and treatment adherence (MMAS-4 score) collected during observational period. Because dependent variable will be collected at each study visit, repeated measures models will be estimated taking into account all available values for dependent and independent variables. Patients could be classified in mild or moderate/severe according to lung function parameters. This will allow to evaluate treatment satisfaction in different groups of patients.

The patients switching treatment during observation period will not be excluded from analysis and will be evaluated at each visit. The patients stopping treatment during study will be censored at last available visit.

#3 To describe the health care resources utilization and related cost during a 12-month observation period

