2.3 Patients evaluable at 12-month follow-up

All enrolled patients meeting the following criteria will be considered evaluable at enrollment and at 12 month follow-up visit:

Patients considered evaluable at enrollment (i.e., responding to criteria of par 2.1 Full Analysis Set) who fulfill also the following criteria (i.e. all FAS patients who performed the 12-month follow-up visit and with at least one Treatment Satisfaction Questionnaire for Medication (TSQM-9) domain score calculated at the 12-month follow-up visit).

Criterion 14: Data collected at 12-month follow-up

- "Data collected at 12 (\pm 1) month follow up?" = "Yes" [F19_PATIENT_DISPOSITION, 12 month f-up.PD_1]

Criterion 15: Follow-up performed 12+/- 1 month from enrollment

- (Date of follow up visit (dd/mmm/yyyy) [F19_PATIENT_DISPOSITION, 12 month f-up.PD_2] – Date of enrolment visit (dd/mm/yyyy) [_PatientInfo. Date_enrollment]/30.4375 \geq 11) AND
- (Date of follow up visit (dd/mmm/yyyy) [F19_PATIENT_DISPOSITION, 12 month f-up.PD_2] – Date of enrolment visit (dd/mm/yyyy) [_PatientInfo. Date_enrollment] /30.4375 \leq 13)

The Biostatistician will evaluate the opportunity to apply a tolerance window during the analysis of data; the Sponsor will be informed of any possible changes in this range.

Criterion 16: patients with at least one Treatment Satisfaction Questionnaire for Medication (TSQM-9) domain score calculated at 12-month follow-up visit

- TSQM-9 items #1,2,3 [TSQM9_1-3] not missing & \neq "Non risponde" at 12-month follow-up, OR
- TSQM-9 items #4,5,6 [TSQM9_4-6] not missing & \neq "Non risponde" at 12-month follow-up, OR
- TSQM-9 items #7,8,9 [TSQM9_7-9] not missing & \neq "Non risponde" at 12-month follow-up

Three sets of patients have been identified for the evaluation of SAT study objectives. Chart 1 displays the analysis sets considered for the statistical analyses foreseen in the Study Protocol.

Chart 1: Sets of patients considered for each statistical analysis

| | Patients evaluable at enrollment (FAS) | Patients evaluable at enrollment and at 6 month follow-up | Patients evaluable at enrollment and at 12 month follow-up |
|--|---|--|---|
| Enrolled and evaluable patients | X | X | X |
| Main socio-demographics and life habits (age, gender, race, education, employment status) at enrollment | X | | |
| Medical history for COPD (number of exacerbations in the 12 months prior to enrollment) | X | | |

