| Patients' satisfaction to COPD medical treatments (by means of the TSQM9) at each study visit | X* | X* | X* |
| Patient disease perception (by means of illness perception questionnaire B-IPQ) at each study visit | X* | X* | X* |
| Patient adherence to COPD treatment (by means of MMAS4) at each study visit | X* | X* | X* |
| Patient health status (by means of CAT questionnaire) at each study visit | X* | X* | X* |
| Measurement of dyspnea (by means of mMRC) at each study visit | X* | X* | X* |
| Patient's COPD awareness (COPD awareness questionnaire) at each study visit | X* | X* | X* |
| Relation between treatment satisfaction and demographic (such as age, gender), clinical (such as number of exacerbations, spirometric parameters) parameters and PROs during a 12-month observation period | | | X |
| Description of health care resources utilization and related cost according to the Italian National Health Service (INHS) during a 12-month observation period. | X | | |
| To assess the correlation between patients' satisfaction and resource utilization during a 12-month observation period | | | X |
| Ongoing pharmacological and non-pharmacological treatments for COPD | X | | |
| Exacerbations occurred during observation period | X | | |

*Patients having PRO score computable at the visit will be considered for this analysis (i.e. PRO filled in at the visit and having a sufficient number of items recorded to allow score computation (PROs computation details are reported in Section 3. "Computed Variables"))).

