4.8 Patients’ COPD awareness

Table 16. Patients’ COPD awareness (Awareness structured interview) each study visit

The table will provide:

- absolute and relative frequencies of patients’ answers to each the COPD awareness questionnaire item [F12_AWARENESS.AWARENESS_01 – AWARENESS_27] at each study visit;
- the descriptive statistics (mean, median, standard deviation, quartiles, min, max) of the COPD awareness questionnaire composite scores (see ‘Computed variables’ chapter) at each study visit.

Changes from enrollment in the COPD awareness composite scores (see ‘Computed variables’ chapter) will be also summarized by visit.

95% confidence intervals limits of the mean will be provided for each estimate.

Descriptives will be calculated over the number of patients respectively evaluable at the time point considered, namely at enrollment (i.e. FAS patients), at 6 months (i.e. evaluable patients at 6 months) and at 12 months (i.e. evaluable patients at 12 months).

4.9 **Relation between treatment satisfaction and demographic/clinical parameters and PROs during 12 month observation period (secondary objective #2)**

The purpose of this secondary analysis is not to obtain a predictive model, but to investigate the relationship among pre-defined variables and outcomes that are of clinical interest. In fact, the intent of this analysis is mainly exploratory and not confirmatory of any a priori hypotheses (consistently with the Study Protocol indications).

Among independent variables in the model, the PROs used in the study are symptomatic tools routinely used in clinical practice to evaluate disease activity and severity (i.e. mMRC and CAT) as per the patient's perspective. Patients' treatment satisfaction could also depend on their clinical status (that would be measured through the mMRC or the CAT) and on their adherence to treatment (MMAS-4 score). This is the reason why the PROs measures are taken into account in exploring the relationship between patient's treatment satisfaction and clinical status.

Contrary to what is stated in paragraph 9.7 of the Study Protocol, the Sponsor on the 12/09/2017 decided not to include the covariates post-baseline in this analysis: therefore, only data collected at enrollment visit will be considered in the mixed models for repeated measures described below, with the exception of the dependent variables (i.e. TSQM-9 scores, that will be considered at each timepoint).

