Table 17. Relation between treatment satisfaction and demographic/clinical parameters and PROs during 12 month observation period (Repeated measures regression models) – Effectiveness domain

A regression model will be estimated; the dependent variable will be the effectiveness domain score of TSQM-9 and the independent ones will be the following:

- age and gender at enrollment;
- number of exacerbations at enrollment;
- relevant spirometry parameters at enrollment (a selection of the following parameter will be done, based on data availability: FEV1, FVC, FEV1 % of the predicted, RV, TLC, DLCO);
- patient's disease severity in terms of level of dyspnea (mMRC score) or CAT total score (depending on data availability) at enrollment (since they are expected to be intercorrelated measures, as reported by 2017 GOLD guidelines, only one of such measures will be considered in the model);
- MMAS-4 score at enrollment.

Center will be included as random effect and study visit (visit1/enrollment, visit2/6months, and visit3/12months) as timepoint.

During data elaboration, the Biostatistician will assess the intercorrelation between the proposed variables, in order to evaluate the opportunity to exclude some of the listed independent variables that are highly associated to each other; in case of important lack of data for certain parameters, such parameters may be excluded as well from the final model.

Because measures referred to the dependent variable will be collected at each study visit, a mixed model for repeated measures will be estimated; moreover, interaction terms between independent variables will be evaluated and, if not significant, they will not be included in the final model. The optimal covariance structure will be evaluated during analysis (preferably "first-order autoregressive correlation" or "unstructured" options). A stepwise selection method will be evaluated during the analysis in order to identify the variables to be included in the final model.

The patients switching treatment during observation period will not be excluded from analysis. The patients stopping treatment during study will be censored at last available visit.

The analysis will be performed considering only evaluable patients at 12 months.

Table 18. Relation between treatment satisfaction and demographic/clinical parameters and PROs during 12 month observation period (Repeated measures regression models) – Convenience domain

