See previous model characteristics: in this analysis, the dependent variable will be the convenience domain score of TSQM-9.

Table 19. Relation between treatment satisfaction and demographic/clinical parameters and PROs during 12 month observation period (Repeated measures regression models) – Global satisfaction domain

See previous model characteristics: in this analysis, the dependent variable will be the global satisfaction domain score of TSQM-9.

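### The objective #2 mixed models exclude FAS patients without an evaluable 12-month visit, against protocol 9.7 and without a declared departure

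*SAP*

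**What the plan says.** **SAP.** Section 4.9 describes the Table 17 model (effectiveness domain) as a mixed model for repeated measures over enrolment, 6 and 12 months, and closes with "The analysis will be performed considering only evaluable patients at 12 months". Table 18 inherits this: "See previous model characteristics: in this analysis, the dependent variable will be the convenience domain score of TSQM-9". Table 19 does the same for global satisfaction. Chart 1 agrees. In its row "Relation between treatment satisfaction and demographic (such as age, gender), clinical (such as number of exacerbations, spirometric parameters) parameters and PROs" only the 12-month column is marked.

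Membership of that set is defined in SAP 2.3. Beyond FAS membership and data collected at month 12, it needs a visit inside the window ("Criterion 15: Follow-up performed 12+/- 1 month from enrollment", with an optional tolerance window left to the Biostatistician). Criterion 16 adds at least one complete TSQM-9 domain at that visit.

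**Protocol.** Section 9.7 says of these same models that "repeated measures models will be estimated taking into account all available values for dependent and independent variables". Its general rules add "Patients with missing values will not be excluded from the analysis, their data will not be replaced" (repeated in 9.13) and "Lost to follow up patients will be analyzed until their last available visit".

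**Declared departure.** SAP 4.9 names one change from protocol 9.7: the sponsor "decided not to include the covariates post-baseline in this analysis". That concerns covariates. The same sentence keeps the TSQM-9 scores at every timepoint.

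**The concern.** A FAS patient with valid scores at enrolment and month 6 but no evaluable month-12 visit contributes nothing to Tables 17-19. A mixed model can use such partial profiles, and the protocol asked for them to be used.

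The set excludes more than drop-outs. A patient seen at 13.5 months also loses the two earlier scores unless the tolerance window is applied. So does an attender with no complete domain at month 12.

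The SAP is also at odds with itself. The Table 17 text censors patients who stop treatment at their last available visit. For a stopper without an evaluable month 12 that sentence has no effect, because the patient is not in the set. Stoppers who do have an evaluable month-12 visit are not affected.

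At stake are precision, possible selection bias in the slopes, and transparency. A reader who sees one departure from 9.7 stated and dated in 4.9 will take it to be the only one.

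**Working it through.** **1. The plan's own figures (protocol 9.5).** Effective sample: 400 × 0.95 = 380 and 400 × 0.80 = 320, as stated. Table 2 uses SE = SD/√N and half-width = 1.96 × SE:
- SD 21.4: 21.4/√380 = 1.098, half-width 2.152; 21.4/√320 = 1.196, half-width 2.345.
- SD 16.6: 16.6/√380 = 0.852, half-width 1.669; 16.6/√320 = 0.928, half-width 1.819.

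All reproduce. They concern the mean global satisfaction score; the documents give no precision target for objective #2.

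**2. Scores lost per model.** Take the 5-20% drop-out as the share without an evaluable month 12, each such patient having one score (enrolment) or two (enrolment and month 6).
- 5%: 400 × 0.05 = 20 patients, 20-40 scores. Share of available scores: 20/(3 × 380 + 20) = 1.7% to 40/(3 × 380 + 40) = 3.4%.
- 20%: 400 × 0.20 = 80 patients, 80-160 scores. Share: 80/(3 × 320 + 80) = 7.7% to 160/(3 × 320 + 160) = 14.3%.

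The true number may be smaller, because protocol 9.5 also counts not-evaluable and not-on-treatment patients in that rate. It may be larger, because Criteria 15 and 16 also remove attenders.

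**3. Precision under random loss.** For the slope of an enrolment covariate, a patient with k scores contributes information proportional to i(k):
- compound symmetry: i(k) = k/(1 + (k−1)ρ);
- AR(1): i(1) = 1, and i(k) = (k − (k−2)ρ)/(1 + ρ) for k = 2, 3.

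With a fraction d lost, SE ratio (12-month set over all available) = √[1 + (d/(1−d)) × i(k)/i(3)]. The correlations 0.4 and 0.6 are assumed.

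| Structure, ρ | i(2) | i(3) | SE rise at 5% loss (k = 1; 2) | SE rise at 20% loss (k = 1; 2) |
|---|---|---|---|---|
| CS, 0.4 | 1.429 | 1.667 | 1.6%; 2.2% | 7.2%; 10.2% |
| CS, 0.6 | 1.250 | 1.364 | 1.9%; 2.4% | 8.8%; 10.9% |
| AR(1), 0.4 | 1.429 | 1.857 | 1.4%; 2.0% | 6.5%; 9.2% |
| AR(1), 0.6 | 1.250 | 1.500 | 1.7%; 2.2% | 8.0%; 9.9% |

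For example, the lowest value at 20% is √(1 + 0.25 × 1/1.857) = 1.065 and the highest is √(1 + 0.25 × 1.250/1.364) = 1.109. This has one covariate and no centre effect, interactions or stepwise selection, so it illustrates the SAP model and does not reproduce it.

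**4. Bias under non-random loss.** This was simulated on assumed inputs: N = 400, SD 21.4, slope −6 per covariate SD, the structures and correlations above, and log-odds of loss of −0.5 or −1 per SD of the last score and between −1 and +1 per SD of the covariate. At 20% loss the 12-month-only slope differed from the all-available slope by −0.45 to +0.73 under the moderate mechanisms, against a slope SE of about 0.8-0.9. Under the two most extreme mechanisms the shifts were −1.29 to −0.79 and +1.23 to +1.91. The all-available slope averaged −5.9 to −6.1 throughout. The sign follows the assumed mechanism, so no direction or bound can be claimed.

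**The case against.** The restriction is openly pre-specified, in 4.9 and again in Chart 1. The analysis is labelled mainly exploratory, has no power target, and under random loss costs only modest precision. SAP 4.2 lets the Biostatistician compare baseline tables across sets to look for selection bias. All of this is fair and limits the importance of the point. It does not reconcile the SAP with protocol 9.7, and the optional comparison restores no scores. The revision history does not mention the analysis set in connection with the regression models. The meeting minutes listed as SAP input are not available here, but a reason recorded there would not be a declaration in the SAP.

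Declaring and justifying the restriction in 4.9 would be a simpler cure. It would repair the transparency but not the lost information.

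Three stronger readings are tempting and unsupported:
- *That the models discard all partial profiles.* They do not. A missed 6-month visit does not exclude a patient from the 12-month set, and patients in that set keep their earlier scores.
- *That the primary result is compromised.* SAP 4.3 computes Tables 10-11 on visit-specific sets.
- *That the slopes will be biased in a known direction.* The documents say nothing on why patients are lost; every bias figure rests on an assumed mechanism.

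**Conclusion.** The point holds and should be fixed. SAP 4.9 and Chart 1 conflict with protocol 9.7 on which patients enter the objective #2 models, and the SAP does not declare it. This rests on the text alone.

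The size is moderate and illustrative: up to about 20-80 patients and 20-160 scores per model at the protocol's drop-out range, and a slope SE larger by about 1.4-2.4% (5% loss) to 6.5-10.9% (20% loss). Those percentages assume random loss, within-patient correlations of 0.4-0.6, and one or two scores per lost patient. Bias is possible if loss depends on earlier scores or covariates, but its direction and size are unknown. The consequence is confined to a secondary, exploratory analysis.

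**What to change.** In SAP 4.9 and Chart 1:
1. Run Tables 17-19 on all FAS patients with the enrolment covariates, using every available score of the modelled domain at enrolment, 6 and 12 months.
2. State that a missing score is omitted for that visit only and leaves the patient's other scores in the model. This is needed because the general rule in SAP section 4 excludes patients with missing data from the analysis of that variable.
3. State that patients who stop treatment contribute scores up to their last available visit, as 4.9 already intends.
4. Settle two remaining differences from protocol 9.7. The FAS requires a TSQM-9 domain score at enrolment (Criterion 10), whereas 9.7 names no visit; and the visit windows drop out-of-window scores. Either include those patients and scores, or declare both as departures in 4.9.
5. Keep the 12-month-evaluable set as a sensitivity analysis, and state the missing-at-random assumption.

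The cost is a few sentences, one Chart 1 edit and three sensitivity runs (one per domain), with no new data and no imputation. The downside is reliance on missing-at-random for the absent scores, which has to be stated openly.

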4.10 Healthcare resource utilization (secondary objective #3)

Table 20. Hospitalizations not in ICU during observation period: patients' distribution

The table will provide:

- distribution of patients by number of hospitalization not in ICU per patient during observation period (see 'Computed variables' chapter);
- descriptive statistics (mean, median, standard deviation, quartiles, min, max) of number of hospitalization not in ICU during observation period per patient (see 'Computed variables' chapter);
- distribution of patients by "Type of admission" ([F10_RESOURCE_CONS. RES_Hosp_matrix_1__Inw - RES_Hosp_matrix_10__Inw]), considering only hospitalization not in ICU according to the field [RES_Hosp_matrix_x__ICU_YN];
- descriptive statistics (mean, median, standard deviation, quartiles, min, max) of total number of days of hospitalization not in ICU per patient (see 'Computed variables' chapter);
- distribution of patients by reasons for hospitalization not in ICU (i.e. "Hospitalization for" [F10_RESOURCE_CONS. RES_Hosp_matrix_1__hos_for - RES_Hosp_matrix_10__hos_for]).

Descriptives and percentages will be computed out of the total number of FAS patients.

Table 21. Hospitalizations not in ICU during observation period: details

The table will provide:

- distribution of hospitalizations not in ICU by "Type of admission" ([F10_RESOURCE_CONS. RES_Hosp_matrix_1__Inw - RES_Hosp_matrix_10__Inw]), considering only hospitalization not in ICU according to the field [RES_Hosp_matrix_x__ICU_YN];
- distribution of hospitalizations not in ICU by reasons for hospitalization (i.e. "Hospitalization for" [F10_RESOURCE_CONS. RES_Hosp_matrix_1__hos_for - RES_Hosp_matrix_10__hos_for]).

Statistics will be computed out of the total number of hospitalizations not in ICU during observation period in FAS patients.

Table 22. Hospitalizations in ICU during observation period: patients' distribution

The table will provide:

- distribution of patients by number of hospitalization in ICU during observation period (see 'Computed variables' chapter);
- descriptive statistics (mean, median, standard deviation, quartiles, min, max) of number of hospitalization in ICU during observation period per patient (see 'Computed variables' chapter);
- distribution of patients by "Type of admission" ([F10_RESOURCE_CONS. RES_Hosp_matrix_1__Inw - RES_Hosp_matrix_10__Inw]), considering only hospitalization in ICU according to the field [RES_Hosp_matrix_x__ICU_YN];
- descriptive statistics (mean, median, standard deviation, quartiles, min, max) of total number of days of hospitalization in ICU (see 'Computed variables' chapter);
- distribution of patients by reasons for hospitalization in ICU (i.e. "Hospitalization for" [F10_RESOURCE_CONS. RES_Hosp_matrix_1__hos_for - RES_Hosp_matrix_10__hos_for]).

Descriptives and percentages will be computed out of the total number of FAS patients.

Table 23. Hospitalizations in ICU during observation period: details

The table will provide:

- distribution of hospitalizations in ICU by "Type of admission" ([F10_RESOURCE_CONS. RES_Hosp_matrix_1__Inw - RES_Hosp_matrix_10__Inw]), considering only hospitalization in ICU according to the field [RES_Hosp_matrix_x__ICU_YN];
- distribution of hospitalizations in ICU by reasons for hospitalization (i.e. "Hospitalization for" [F10_RESOURCE_CONS. RES_Hosp_matrix_1__hos_for - RES_Hosp_matrix_10__hos_for]).

Statistics will be computed out of the total number of hospitalizations in ICU during observation period in FAS patients.

Table 24. Emergency room accesses: patients' distribution

The table will provide:

- distribution of patients by number of ER accesses during observation period per patient (see 'Computed variables' chapter);

- descriptive statistics (mean, median, standard deviation, quartiles, min, max) of number of ER accesses during observation period per patient (see 'Computed variables' chapter);
- distribution of patients by reasons of ER admission (i.e. "Admission for" [F10_RESOURCE_CONS.RES_ER_matrix_1_adm_for - RES_ER_matrix_12_adm_for]).

Descriptives and percentages will be computed out of the total number of FAS patients.

Table 25. Emergency room accesses: details

The table will provide:

- distribution of reasons of ER accesses during observation period (i.e. "Admission for" [F10_RESOURCE_CONS.RES_ER_matrix_1_adm_for - RES_ER_matrix_12_adm_for]).

Statistics computed over the total number of ER accesses during observation period in FAS patients.

Table 26. Specialist outpatient visits: patients' distribution

The table will provide:

- descriptive statistics (mean, median, standard deviation, quartiles, min, max) of the total number of specialist outpatient visits per patient during observation period (see 'Computed variables' chapter);
- distribution of patients by number of specialist outpatient visits per patient during observation period (see 'Computed variables' chapter);
- distribution of patients by type of specialist outpatient visits performed during observation period (i.e. "Specialist" [F10_RESOURCE_CONS.Specialist]);
- distribution of patients by reasons of specialist outpatient visit (i.e. "Visit for" [F10_RESOURCE_CONS.RES_Visit_for]).

Descriptives and percentages will be computed out of the total number of FAS patients.

Table 27. General practitioner visits: patients' distribution

The table will provide:

- distribution of patients by total number of general practitioner visits per patient during observation period (see 'Computed variables' chapter);
- descriptive statistics (mean, median, standard deviation, quartiles, min, max) of the total number of general practitioner visits per patient during observation period (see 'Computed variables' chapter).

Descriptives and percentages will be computed out of the total number of FAS patients.

Table 28. Laboratory tests: patients' distribution

The table will provide:

- distribution of patients by total number of laboratory test per patient during observation period (see 'Computed variables' chapter);
- descriptive statistics (mean, median, standard deviation, quartiles, min, max) of total number of laboratory test per patient during observation period (see 'Computed variables' chapter);
- distribution of patients by type of test/examination during observation period (i.e. "Test/examination" [F10_RESOURCE_CONS.RES_Lab_matrix_1_Test - RES_Lab_matrix_20_Test]);
- distribution of patients by reasons of test/examination (i.e. "Test/examination for" [F10_RESOURCE_CONS.RES_Lab_matrix_1_for - RES_Lab_matrix_20_for]).

Descriptives and percentages will be computed out of the total number of FAS patients.

Table 29. Laboratory tests: details

The table will provide:

- frequency of each type of test/examination during observation period (listed in field "Test/examination" [F10_RESOURCE_CONS.RES_Lab_matrix_1_Test - RES_Lab_matrix_10_Test] and according to the number of tests recorded in field "N° of tests" [F10_RESOURCE_CONS.RES_Lab_matrix_1_num - RES_Lab_matrix_20_num]),
- distribution of reasons of test/examination (i.e. "Test/examination for" [F10_RESOURCE_CONS.RES_Lab_matrix_1_for - RES_Lab_matrix_20_for]).

Statistics computed over the total number of Laboratory tests during observation period in FAS patients.

Table 30. Oxygen therapy

The table will provide:

- Absolute and relative frequency of Patients with oxygen therapy during the observational period (see 'Computed variables' chapter)

Percentages will be computed out of the total number of patients evaluable for the FAS.

Table 31. List of oxygen therapies

List of the following variables:

- Patient ID
- "Date of enrollment visit" [[_PatientInfo.Date_enrollment](#)]
- "Kind of therapy" [[F21_OXYGEN_THERAPY.KIND_OF_THER](#)]
- "Drug" [[F21_OXYGEN_THERAPY.DRUG](#)]
- "Flow (L/min)" [[F21_OXYGEN_THERAPY.FLOW](#)]
- "Hours per day" [[F21_OXYGEN_THERAPY.HOURS](#)]
- "Start date of therapy" [[F21_OXYGEN_THERAPY.START_DATE_NF](#)]
- "Ongoing" [[F21_OXYGEN_THERAPY.ONGOING_NF_THER](#)]
- "End date of therapy" [[F21_OXYGEN_THERAPY.END_DATE_NF](#)]
- "Therapy for" [[F21_OXYGEN_THERAPY.NF_THER_FOR](#)]

Only patients evaluable for the FAS will be considered.

Table 32. Patients receiving fixed/non-fixed dose therapies for COPD at enrollment

The table will provide:

- distribution of patients with COPD pharmacological fixed dose therapy at enrollment (see 'Computed variables' chapter);
- distribution of patients with COPD pharmacological non-fixed dose therapy at enrollment (see 'Computed variables' chapter);
- distribution of patients receiving both COPD pharmacological fixed and non-fixed therapy at enrollment (see 'Computed variables' chapter).

Percentages will be computed out of the total number of patients evaluable for the FAS.

Table 33. COPD pharmacological treatments ongoing at enrollment

The table will provide:

- distribution of COPD pharmacological treatments (classes) ongoing at enrollment (see 'Computed variables' chapter).

Percentages will be computed out of the total number of patients evaluable for the FAS.

Table 34. COPD pharmacological treatments ongoing at 6-month follow-up visit

The table will provide:

- distribution of COPD pharmacological treatments (classes) ongoing at 6-month follow-up visit (see 'Computed variables' chapter)

Percentages will be computed out of the total number of patients evaluable for the FAS.

Table 35. COPD pharmacological treatments ongoing at 12-month follow-up visit

The table will provide:

- distribution of COPD pharmacological treatments (classes) ongoing at 12-month follow-up visit (see 'Computed variables' chapter)

Percentages will be computed out of the total number of patients evaluable for the FAS.

Table 36. Medications for adverse events

The table will provide the distribution of patients according to the field "Therapy for the event" [[F22_AES_AND_ADRS.AE_THERAPY](#)] (i.e. patients who received medications for adverse events during the study).

Percentages will be computed out of the total number of patients evaluable for the FAS.

4.11 Correlation between patients' satisfaction and resource utilization (secondary objective #4)

Table 37. Correlation between patients' satisfaction and resource utilization (including drugs)

A correlation index (Pearson or Spearman) will be computed between TSQM-9 subscales scores (as defined in "Computed variables" chapter) at 12 month follow-up visit and the number of hospitalizations per patient during observation period (as defined in "Computed variables" chapter); p-value will be provided as well.

A correlation index (Pearson or Spearman) will be computed between TSQM-9 subscales scores (as defined in "Computed variables" chapter) at 12 month follow-up visit and the number of ER accesses per patient during observation period (as defined in "Computed variables" chapter); p-value will be provided as well.

A correlation index (Pearson or Spearman) will be computed between TSQM-9 subscales scores (as defined in "Computed variables" chapter) at 12 month follow-up visit and the number of specialist visits per patient during observation period (as defined in "Computed variables" chapter); p-value will be provided as well.

A correlation index (Pearson or Spearman) will be computed between TSQM-9 subscales scores (as defined in "Computed variables" chapter) at 12 month follow-up visit and the number of general practitioner visits per patient during observation period (as defined in "Computed variables" chapter); p-value will be provided as well.

A correlation index (Pearson or Spearman) will be computed between TSQM-9 subscales scores (as defined in "Computed variables" chapter) at 12 month follow-up visit and the number of laboratory test per patient during observation period (as defined in "Computed variables" chapter); p-value will be provided as well.

A correlation index (Pearson or Spearman) will be computed between TSQM-9 subscales scores (as defined in "Computed variables" chapter) at 12 month follow-up visit and the number of therapies administered for COPD per patient during observation period (as defined in "Computed variables" chapter); p-value will be provided as well.

A correlation index (Pearson or Spearman) will be computed between TSQM-9 subscales scores (as defined in "Computed variables" chapter) at 12 month follow-up visit and the number of therapies administered for COPD-related adverse events and COPD exacerbations per patient during observation period (as defined in "Computed variables" chapter); p-value will be provided as well.

